HRPO Protocol

1) Protocol Title (Version # and/or Version Date)

The Emotions and Decisions of Couples, #12-433, v. 06/13/2018

2) IRB Review History

N/A

3) Objectives

The proposed study is an experimental comparison of the effects of alcohol on arousal and emotion-regulation between 112 Distressed Violent (DV) and 112 Distressed Nonviolent (DNV) partners. One partner from each DV couple will be pseudo-randomly selected and yoked to a DNV partner of the same sex and a relationship satisfaction within a five-point range for participation in the experiment. To test the overall hypothesis that over-arousal is a mechanism through which alcohol is associated with increases in the frequency and severity of IPV, the selected partners will participate in a counter-balanced placebo session and alcohol administration session during which EEG, psychophysiology and pupillary response measurements of arousal will be collected during an emotion regulation task.

Specific Aim 1: To determine if normal increases in arousal after alcohol exposure is potentiated by evocative partner stimuli is greater for distressed violent (DV) partners compared to distressed nonviolent (DNV) partners. *Hypothesis 1a:* DV and DNV partners will experience comparable alcohol related increases in arousal. *Hypothesis 1b:* DV partners will demonstrate greater arousal increases by evocative partner displays than DNV partners. *Hypothesis 1c:* DV partners will experience greater arousal when exposed to alcohol and evocative partner stimuli than DNV partners.

Specific Aim 2: To determine if alcohol induced arousal interferes with DV partners' ability to regulate emotion in response to evocative partner stimuli compared to DNV partners. *Hypothesis 2a:* Emotion regulation during evocative stimuli will be reduced compared to neutral stimuli. *Hypothesis 2b:* Emotion regulation during evocative stimuli will be reduced by alcohol. *Hypothesis 2c:* DV partners will be less able to regulate emotion during evocative stimuli than DNV partners. *Hypothesis 2d:* Alcohol will interfere with DV partners' ability to regulate emotion during evocative stimuli compared to DNV partners.

4) Background

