DV couples also express higher levels of negative affect, such as contempt and belligerence, which escalate conflict beyond that seen in DNV couples (Gottman et al., 1995). Compared to DNV couples, DV couples become more psychologically abusive, emotionally aggressive and increasingly physiologically aroused as their conflict continues because of these patterns (Babcock et al., 1993; Frye & Karney, 2006; Gottman, et al., 1995; Jacobson, et al., 1994). Furthermore, verbal aggression and physical aggression are highly correlated in couples (Lundeberg, Stith, Penn & Ward, 2004) with 94% of those reporting physical aggression also

reporting verbal aggression (Shook, Gerrity, Jurich & Segrist, 2000). DV couples also have difficulty disengaging from conflict once it begins without escalating to physical aggression due in part to their highly aroused state (Ekman, 1984; Frye & Karney, 2006; Gottman, 1994; Jacobson, et al., 1994; Margolin, John & Foo, 1998; O'Leary, 1999). These findings suggest that DV couples are unable to regulate their emotional responses in the face of evocative conflict. Furthermore, partners in relationships whose conflict chronically generates such arousal become hypervigilant to potentially threatening and escalating interactions, and are more likely to misattribute threat potential to relatively neutral or positive acts (Gottman, 1994). These findings also suggest a sensitization process whereby repeated exposures to aversive dyadic interactions result in a progressive amplification of the arousal response to the partner's behavior.

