Specific Aim 1: To determine if normal increases in arousal after alcohol exposure is potentiated by evocative partner stimuli and is greater for DV partners compared to DNV partners. We will conduct a 2 (beverage condition: alcohol vs. placebo) x 2 (stimulus: evocative vs. neutral) repeated measures ANOVA with a between-subjects factor (partner type: DV vs. DNV). To test whether alcohol increases overall arousal (**Hypothesis 1a**), we will examine the main effect of alcohol vs. placebo on arousal variables, collapsing across partners and stimuli during the WATCH condition as alcohol should effect the arousal of both partner types equally. To test whether DV partners are more aroused by evocative partner displays than DNV partners (**Hypothesis 1b**), we will test the interaction effect of partner type and stimulus type, collapsing across alcohol and placebo conditions. Finally, to test the hypothesis that alcohol induced increases in arousal above placebo will be greater for evocative than neutral stimuli (**Hypothesis 1c**) for DV vs. DNV partners, we will test the three-way interaction in the 2 (DV vs. DNV) x 2 (alcohol vs. placebo) x 2 (evocative vs. neutral) repeated measures ANOVA. Specifically, this contrast will examine the effect of partner type when comparing stimuli type (evocative) to beverage condition (alcohol) on arousal and provides a critical control given that conflict intensity may differ between DV and DNV couples. The 3-way interaction (Hyp1c) will allow us to be able to determine whether the change in arousal between alcohol and placebo sessions for the evocative stimuli differs between couple types. The arousal level of evocative stimuli is matched between alcohol and placebo sessions, thus allowing for a controlled examination of alcohol-induced increases in arousal for evocative stimuli across DV and DNV couples.

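### The plan reads the Hypothesis 1c three-way interaction as a group difference for evocative clips alone, which that term does not estimate, and no test of that difference is planned

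*Combined protocol and SAP*

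**What the plan says.** H1c appears in three forms.

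- **Section 3 (Objectives):** "DV partners will experience greater arousal when exposed to alcohol and evocative partner stimuli than DNV partners". There is no neutral comparator and no explicit placebo comparator.
- **Section 14, Data Analysis Plan, Specific Aim 1, opening statement of H1c:** "alcohol induced increases in arousal above placebo will be greater for evocative than neutral stimuli", for DV against DNV partners. The named test is the partner type x beverage x stimulus interaction in the repeated measures ANOVA.
- **Same paragraph, on what that interaction shows:** "The 3-way interaction (Hyp1c) will allow us to be able to determine whether the change in arousal between alcohol and placebo sessions" is different in the two couple types when the clips are evocative. The paragraph's closing sentence again speaks of the alcohol effect for evocative clips across couple types, without neutral clips.

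Hypothesis 1a (H1a) bears on this: "DV and DNV partners will experience comparable alcohol related increases in arousal". Its only named test is the main effect of beverage, pooled over partner types and stimuli. No beverage x partner-type test is named, either within evocative clips or overall.

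**The concern.** The second and third forms are different quantities. The second is a difference between clip types in the group difference; the third is the group difference for one clip type. Only the second is what a three-way interaction estimates.

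An analyst who follows the plan's interpretation could err in two directions. A null interaction could be reported as no group difference in the alcohol effect for evocative clips when there is one. A significant interaction could be reported as such a difference when it arises only from the neutral clips. The plan promises an answer about evocative clips and contains no named test that gives it.

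**Working it through.** **Inputs.** Group sizes come from section 3: "between 112 Distressed Violent (DV) and 112 Distressed Nonviolent (DNV) partners". The plan gives no significance level, effect size, SD or correlation for these tests, and no power figure to reproduce. Assumed for illustration: two-sided 0.05, cell SD 1, no dropout, and correlations as stated below.

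**Step 1: the contrasts.** With A = alcohol and P = placebo:

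- dE = (A - P, evocative, DV) - (A - P, evocative, DNV)
- dN = (A - P, neutral, DV) - (A - P, neutral, DNV)
- three-way term = dE - dN
- beverage x partner type, averaged over clips = (dE + dN)/2

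The plan's opening statement of H1c is dE - dN. Its interpretive sentence is dE. They coincide in value only when dN = 0. This step needs no assumed figure.

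**Step 2: worked cases.** Rejection rates are from 4,000 simulated trials per case, 112 per group, all four cells correlated 0.5.

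| Case | A - P in DV (evoc., neut.) | A - P in DNV (evoc., neut.) | dE | dN | Three-way | Reject dE | Reject three-way | Reject beverage x partner type |
|---|---|---|---|---|---|---|---|---|
| 1 | 0.7, 0.2 | 0.2, 0.2 | 0.5 | 0 | 0.5 | 96% | 75% | 74% |
| 2 | 0.7, 0.7 | 0.2, 0.2 | 0.5 | 0.5 | 0 | 96% | 5% | 100% |
| 3 | 0.7, 0.2 | 0.7, 0.7 | 0 | -0.5 | 0.5 | 5% | 75% | 75% |
| 4 | 0.7, 0.2 | 0.45, 0.45 | 0.25 | -0.25 | 0.5 | 46% | 75% | 5% |

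Cases 2 and 3 are the two errors. In case 4, H1a holds on average over clips (dE + dN = 0). The three-way term is then 2dE, so it is zero only when dE is zero, but it is twice the size of dE.

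**Step 3: precision.** Let r_w be the correlation between clip types within a session and r_c the correlation across sessions (taken as the same for like and unlike clips). The per-person contrast variances are V_E = 2(1 - r_c) for the evocative contrast and V_3 = 4(1 - r_w) for the three-way term. Each SE is sqrt(V x 2/112). With all correlations 0.5, SE_E = sqrt(1 x 2/112) = 0.134 and SE_3 = sqrt(2 x 2/112) = 0.189. The differences detectable with 80% power are 2.80 x 0.134 = 0.37 and 2.80 x 0.189 = 0.53.

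Set dE so that its own contrast has 80% power, and let k = dN/dE. The three-way z is 2.80 x (1 - k) x sqrt(V_E/V_3), and power is Φ(z - 1.96) + Φ(-z - 1.96).

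| Assumed r_w, r_c | SE_3/SE_E | k = 0 | k = 0.25 | k = 0.5 | k = 1 |
|---|---|---|---|---|---|
| equal (any common value) | 1.41 | 51% | 32% | 17% | 5% |
| 0.6, 0.5 | 1.26 | 60% | 38% | 20% | 5% |
| 0.75, 0.5 | 1.00 | 80% | 56% | 29% | 5% |
| 0.8, 0.5 | 0.89 | 88% | 65% | 35% | 5% |

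The power at k = 0 moves from 51% to 88% with the correlations. The 5% at k = 1 does not move, because it is Step 1 restated.

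**The case against.** **The test itself is right.** A reader might infer that the three-way interaction is the wrong test of H1c, or that it can be zero when H1c is true. The documents do not support that for H1c as the analysis plan defines it: the three-way contrast is that hypothesis. Aim 1 asks whether evocative stimuli potentiate the alcohol effect, which needs a neutral comparator. If alcohol raised DV arousal equally for both clip types, a null interaction would answer that question correctly. This objection stands, and it confines the fault to the interpretive sentence, the Objectives wording and the missing contrast.

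**The failure cases conflict with H1a.** Case 2 needs a DV-specific alcohol effect on neutral clips as large as that on evocative clips. That stands too, and so the case should not be called likely. But the beverage main effect cannot reveal a departure from equal alcohol effects. The factorial model contains the beverage x partner-type term, yet the plan does not name it as a test.

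**The background does not make the failure likely.** Section 4 says such partners "are more likely to misattribute threat potential to relatively neutral or positive acts", and a reader might take this as evidence that dN is not zero. It says nothing about alcohol. A group difference on neutral clips that is the same in both sessions cancels in alcohol minus placebo.

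**A loss of power is not established.** A reader might take the 51% figure as the price of the three-way term. It holds only when the cells are independent or equally correlated. Section 11 shows both clip types in the same session and puts the beverages in separate sessions, so session-level noise may cancel in the three-way term and not in the evocative contrast. In the last row above the three-way term is the more precise of the two.

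**Conclusion.** The point holds as a mismatch between a planned test and its stated meaning. The three-way term tests whether the group difference in alcohol effect is specific to evocative clips. It does not establish the group difference for evocative clips, and no planned test does. This is algebra and rests on no assumption.

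The practical size depends on dN, which the documents do not give. The two quantities agree if dN = 0. They disagree completely in cases 2 and 3 (96% against 5%, and 5% against 75%, under the stated assumptions), both of which depart from H1a. All power values are illustrations.

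A null three-way result would mean that H1c is not supported. It would not mean that H1c has been rejected, nor that the groups respond alike to evocative clips under alcohol.

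**What to change.** 1. Keep the three-way interaction as the test of H1c, described as a test of specificity to evocative stimuli.
2. Correct the interpretive sentence in the Specific Aim 1 analysis, and the closing sentence that repeats its reading, so that the neutral comparator is stated.
3. Reword H1c in section 3 to match the analysis plan.
4. Prespecify, from the same model, the beverage x partner-type contrast within evocative WATCH trials. Base any claim about evocative clips alone on that contrast and not on the three-way term.
5. Report alongside it the same contrast for neutral clips and the overall beverage x partner-type term, so that a departure from H1a is visible.

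The three-way test should not be made conditional on the new contrast. That would put the plan's own H1c test behind one that cannot show potentiation, and H1c could go untested.

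The cost is wording changes in two sections and one additional planned contrast. No new data or procedures are needed. If power is quoted, give it over a range of within-session and cross-session correlations.

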Participants will be a convenience sample of 112 DV couples and 112 DNV couples residing in the greater Albuquerque, NM metro area. Eligible couples will be 1) English-speaking, 2) heterosexual or homosexual, 3) between the ages of 21 and 45, and will provide informed consent. Because this is a study of the role of alcohol in IPV, all participants (DV & DNV) must 4) be in a distressed relationship (Revised Dyadic Adjustment Scale score below 47), 5) consume at least one to two alcoholic drinks per sitting each week for females and three to four alcoholic drinks for males, 6) report two binge drinking episodes (>4 drinks for males, >3 drinks for females) in month prior to assessment, 7) be married or cohabitating for at least six months, 8) both partners must be willing to participate, 9) must have a breath alcohol level of 0.0 g% at all visits. DV couples must have a history of at least mild physical aggression in the past six months (e.g., twisted partner's arm or hair). Participants will be excluded if they are/have 1) currently separated, 2) an order of protection in place, 3) facing violence-related criminal charges, 4) currently in a domestic violence shelter, 5) evidence of psychosis or severe personality disturbance, 6) pregnant, 7) taking a medication contraindicated for use with alcohol, 8) currently taking insulin or oral hypoglycemic medication, 9) an AUDIT score greater than 19 indicating alcohol dependence, 10) illicit drug use (except marijuana), or 11) provide a positive UA at first emotion-regulation session. Participants will be screened for psychosis and severe personality disturbance using the SCID II psychosis and personality screeners. The age range reflects legal drinking age and age range used in other studies of alcohol and IPV (Eckhardt, 2007). The minimum length of relationship is to obtain a representative sample of DV couples. DV relationships are exceptionally unstable and dissolve at rates many times that of DNV relationships (Gortner et al., 1997). It is feared that older DV relationships may not be representative of DV relationships (e.g., less violent, Cui et al., 2013).

Adults unable to consent, individuals who are not yet adults, pregnant women and prisons will be excluded.

6) Number of Subjects (Recruitment Target)

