Two hundred twenty-four (112 Distressed Violent and 112 Distressed NonViolent) couples will be enrolled in the study. We will screening 1200 couples in order to obtain the number to be enrolled in the study.

7) Recruitment Methods

Recruitment will be conducted using strategies discussed in Holtzworth-Munroe et al. (1992) for recruiting distressed violent couples (e.g., advertising for distressed couples) and will be conducted at the couple level. The Albuquerque, NM metropolitan area has a population of approximately 900,000, which is sufficiently large for the recruitment of a specialized sample. No recruitment will take place in domestic violence shelters, court mandated treatment settings, or through court referrals. Evidence suggests that individuals recruited from these locations are more likely to be generally violent (violence outside the family), have severe personality disturbances (antisocial personality

disorder), and have involvement in other criminal activity (1992). Participants will be recruited via advertisements placed throughout the Albuquerque Metro area, local newspapers, online forums, list serves, radio spots and television interviews. In addition, advertisements will be placed on ResearchMatch.org. Because of concerns about an invasion of privacy and the sensitivity of the data collected in this study, flyers will refer to generic aspects of relationship dissatisfaction and alcohol consumption.

In advertising for couples who drink alcohol weekly we have determined that this statement on the recruitment flyer or ad is selecting, almost exclusively, for individuals who have an alcohol use disorder or who are alcohol dependent, and therefore ineligible for our study. We are requesting permission to also place advertisements that do not include the “drink alcohol weekly” aspect of the inclusion criteria in the ad. The ad will continue to indicate that participants may consume alcohol during one or both experimental session, and we will continue screen for alcohol use consistent with our inclusion criteria (AUDIT score no greater than 19 and two binge episodes in previous month). (Please see the attached versions of the advertisement for the recruitment script and for how posted flyers will appear.)

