Specific Aim 2: To determine if alcohol induced arousal interferes with DV partners' ability to regulate emotion in response to evocative partner stimuli compared to DNV partners. All hypotheses will be tested using a 2 (beverage condition: alcohol vs. placebo) x 2 (stimulus: evocative vs. neutral) x 2 (regulation condition: WATCH vs. DON'T REACT) repeated measures ANOVA with a between-subjects factor (partner type: DV vs. DNV). Testing specific interactions within the overall model will test each hypothesis. If the ages of the DV and DNV partners are significantly different, ANCOVAs will be conducted as age may further moderate the relationships tested in Aim 2. To test the hypothesis that emotional regulation during evocative partner stimuli will be reduced compared to regulation during neutral stimuli (**Hypothesis 2a**), we will test the 2 (evocative vs. neutral) x 2 (WATCH vs. DON'T REACT) interaction term, collapsing across partner type in the placebo condition. To test the hypothesis

that emotion regulation during evocative partner stimuli will be reduced by alcohol, (**Hypothesis 2b**) we will test the 2 (evocative vs. neutral) x 2 (WATCH vs. DON'T REACT) interaction term collapsing across partner type in the alcohol condition. To test the hypothesis that DV partners are less able to regulate emotion during evocative stimuli than the DNV partners (**Hypothesis 2c**), we will test the 2 (DV vs. DNV) x 2 (evocative vs. neutral) x 2 (WATCH vs. DON'T REACT) in the placebo condition. Finally, to test the hypothesis that alcohol interferes with the ability to regulate emotion for DV partners compared to DNV partners (**Hypothesis 2d**), we will test the 2 (DV vs. DNV) x 2 (alcohol vs. placebo) x 2 (evocative vs. neutral) x 2 (WATCH vs. DON'T REACT) interaction.

15) **Provisions to Monitor the Data to Ensure the Safety of Subjects**

1. The experienced and qualified professionals responsible for determining serious adverse events in the proposed study “Emotions and Decisions of Couples” will be the PI and co-Investigator for the study [name]. and [name]. [name] has experience with both oral and intravenous alcohol administration and will work with [name] to identify any adverse events.

Any serious adverse events that do occur during the course of the study will immediately be reported to the University of New Mexico Human Research Protections Office as an adverse event.

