The investigators have the right to end any participant's participation in this study if it is determined that the participant no longer qualifies to take part, does not follow study procedures, or if it is in best interest of the participant, that of the participant's partner, or the study's best interest to stop your participation. The Principal Investigators may stop the study at any time.

17) **Risks to Subjects**

Risks Associated with Study Participation:

1. There is an uncommon risk of boredom or intrusiveness pertaining to the completion of measures pertaining to the couples' relationship functioning and drinking.
2. There is a common risk of some participants becoming slightly intoxicated that may lead to temporary impairment in motor coordination as a result of consuming alcohol.
3. There is a common risk of discomfort to participants in discussing an area of ongoing disagreement with their partner.
4. There is a rare, but serious risk of partner violence occurring after participating in the discussion of an area of disagreement and after viewing task stimuli in subsequent visits.
5. There is also a rare, but serious risk of a loss of confidentiality and privacy that includes the identification of participants by their video image, an invasion of privacy, social and economic risks, alterations in relationships with others that are to the disadvantage of the participant,

embarrassment, loss of respect of others, labeling with negative consequences or diminishing the participant's opportunities and status in relation to others.

6. There is also the risk of unanticipated risks.

Protection Against Risks Associated with Study Participation:

1. To protect against the risk of boredom or intrusiveness, we will provide breaks to the participants during the completion of study measures. The interviewers are also trained in discussing sensitive material with clinical research participants. If a participant finds a topic uncomfortable, they will be able to skip those questions or discontinue their participation.

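### The repeated-measures ANOVAs by default drop anyone with only one beverage session; a mixed model on all completed sessions would keep those data and limit bias if loss differs between groups

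*Combined protocol and SAP*

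**What the plan says.** Section 14 (Data Management, Data Analysis Plan) specifies for Aim 1 a beverage-by-stimulus "repeated measures ANOVA with a between-subjects factor (partner type: DV vs. DNV"). Aim 2 adds regulation condition as a third within-person factor: "All hypotheses will be tested using a 2 (beverage condition: alcohol vs. placebo") and the other factors. It then says: "Testing specific interactions within the overall model will test each hypothesis".

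Three Aim 2 hypotheses concern a single session. H2a is a stimulus-by-regulation term, "collapsing across partner type in the placebo condition". H2c, that "DV partners are less able to regulate emotion during evocative stimuli than the DNV partners", is also confined to placebo. H2b is confined to alcohol. H1b averages over both beverages. H1c and H2d compare the two sessions.

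Section 11 (Study Methods) places the sessions on two separate visits in counterbalanced order. Participation can end between them in several ways:

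- voluntary withdrawal at any time (Section 16);
- a stop by the investigators, among other reasons "if it is determined that the participant no longer qualifies to take part" (Section 16);
- a positive pregnancy test on either experimental day (Section 15);
- a breath alcohol reading above zero at any visit (Section 5);
- a request to delete the video (Sections 11, 16 and 28).

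The documents give no missing-data method, analysis set, drop-out allowance, replacement rule or interval between sessions. Multilevel modelling appears only as staff training, in Section 23 (Resources Available).

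**The concern.** A conventional repeated-measures ANOVA needs every within-person cell filled. Someone who attends one session has half the cells empty and drops out of the whole model. If H2a, H2b and H2c are terms of that model, the loss includes people whose data for those hypotheses are complete: placebo-first participants for H2a and H2c, alcohol-first participants for H2b.

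The larger risk is selection. The DV-DNV contrasts become completer comparisons. If people who react strongly in the first session return less often, and more DV than DNV partners are lost, the remaining DV group is calmer than the group tested at the first session, and the group difference is understated. Section 5 makes unequal loss plausible, since it says that "DV relationships are exceptionally unstable and dissolve at rates many times that of DNV relationships".

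**Working it through.** **Inputs from the documents.** Section 6: "Two hundred twenty-four (112 Distressed Violent and 112 Distressed NonViolent) couples will be enrolled in the study", that is 112 + 112 = 224, with one partner per couple tested. Order is counterbalanced, so about half have placebo first. No alpha, power, effect size, SD or loss rate is stated, so there is no planned power figure to reproduce. Everything below on loss is assumed.

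**Who is lost.** Take 20% DV and 10% DNV loss between sessions. Completers: 112 × 0.80 ≈ 90 DV and 112 × 0.90 ≈ 101 DNV, total 191, so 33 of 224 are dropped. People with a placebo session: 112 × 0.90 ≈ 101 and 112 × 0.95 ≈ 106, total 207. So 207 − 191 = 16 of the 33 have complete placebo data for H2a and H2c. The rest have an alcohol session usable for H2b.

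**Precision of H2c.** With a fraction d lost in each group, completers number 112(1 − d) per group and placebo sessions 112(1 − d/2). The standard-error ratio is √[(1 − d/2)/(1 − d)]:

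- d = 10%: √(0.95/0.90) = 1.027
- d = 20%: √(0.90/0.80) = 1.061

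For scale, take a standardised effect of 0.374, which gives 80% power at 112 per group (two-sided 0.05, assumed). At 20%/20% loss, power is 70.9% with completers and 75.8% with all placebo sessions. At 20%/10% it is 73.3% and 76.8%.

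**Bias in a contrast averaged over sessions (H1b).** Simulation assumptions: true DV-DNV difference 0.50 SD; correlation ρ of the within-session contrast between sessions 0.3 to 0.7; log-odds of loss rising by b = 0.5 to 1.0 per SD of first-session response.

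| Loss DV/DNV | Completers | Likelihood analysis, all sessions |
|---|---|---|
| 15%/5% | 0.43 to 0.47 | about 0.50 |
| 30%/10% | 0.36 to 0.44 | about 0.50 |
| 15%/15% | 0.50 | 0.50 |

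A hand check: to first order, losing a fraction p lowers the retained first-session mean by b·p and the second-session mean by ρ·b·p. The completer difference is then about 0.50 − b(p_DV − p_DNV)(1 + ρ)/2.

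- 15%/5%, b = 0.5, ρ = 0.3: 0.50 − 0.5 × 0.10 × 0.65 = 0.468
- 15%/5%, b = 1.0, ρ = 0.7: 0.50 − 1.0 × 0.10 × 0.85 = 0.415
- 30%/10%, the same two corners: 0.435 and 0.330

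The approximation somewhat overstates the bias when b is large. It shows why equal loss gives none: the term p_DV − p_DNV is zero.

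**Bias in H2c.** A second simulation used 112 per group, half placebo first, true difference 0.375, ρ = 0.5 and b = 1. Completers gave 0.38 at 10%/10% loss, 0.32 at 20%/10% and 0.25 at 30%/10%. The likelihood analysis gave 0.38, 0.38 and 0.37.

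**Which mixed model.** A participant intercept and a participant-by-session effect both cancel from a within-session contrast such as evocative minus neutral. A model with only these treats a person's two session contrasts as independent. If each has variance σ², their mean has variance σ²(1 + ρ)/2, but the model uses σ²/2. The effective critical value for H1b is then 1.96/√(1 + ρ), or 1.72, 1.60 and 1.50 at ρ = 0.3, 0.5 and 0.7. The two-sided type I error is about 9%, 11% and 13%, which simulation with complete data confirmed. The ANOVA held about 5%. This reduced model also recovers less of the bias, giving 0.47 to 0.49 at 15%/5% and 0.44 to 0.48 at 30%/10%, because it ignores the between-session correlation.

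**The case against.** Several points on the other side are sound.

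- **Deletion is not a stated rule.** A reader might infer that the plan orders one-session participants to be dropped. It does not. Dropping them is how the named method works by default, and the plan names no alternative.
- **H2a to H2c could be separate ANOVAs.** Each is worded as a term within one beverage condition. A single-session ANOVA is a possible reading and would keep those data. The statements that all hypotheses use the full factorial, and are tested as terms of the overall model, point the other way. Even the favourable reading does not help H1b.
- **The instability sentence is not a drop-out forecast.** A reader might infer that the plan expects more DV loss between visits. The sentence justifies the minimum relationship length. The selected partner attends these sessions individually, and stopping someone who separates between visits is an inference from the exclusion list, not a written rule. The sentence makes unequal loss plausible and no more.
- **The effect is modest and conditional.** The loss rates, their ratio and the dependence on response are all assumed. The precision cost is small. H1c and H2d compare sessions, so one-session data add little to them. Data that a participant asks to have withdrawn may be lost under any method.
- **A careless mixed model would do harm.** With complete data the ANOVA's H1b test is valid, and a model with too few random effects would spoil it. This settles how the replacement must be specified. It is not a reason to keep complete-case analysis.

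**Conclusion.** The concern holds in limited form. Both aims rely on a method that by default uses only participants with both sessions. The plan allows for partial participation and gives no missing-data rule. Read with the overall-model statement, this also discards usable single-session data for H2a, H2b and H2c. About half of those lost between sessions would have complete placebo data.

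The precision cost for H2c is about 3% to 6% on the standard error at 10% to 20% loss. The main issue is possible understatement of DV-DNV contrasts such as H1b: 0.43 to 0.47 at 15%/5% loss and 0.36 to 0.44 at 30%/10%, against a true 0.50 SD. This requires loss that is both unequal by group and related to the first-session response. The documents neither establish nor exclude either condition. The change is worth making because it is cheap and can be made before the data are examined.

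**What to change.** In the Aim 1 and Aim 2 paragraphs of the Data Analysis Plan, replace the repeated-measures ANOVAs with linear mixed models that have the same fixed factors and interactions, fitted by REML to every completed session.

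- **Covariance.** Use an unstructured within-person covariance over the cell means. With four cells in Aim 1 this has 4 × 5/2 = 10 parameters; with eight in Aim 2, 8 × 9/2 = 36. If it does not converge, use a participant random intercept plus participant-by-beverage, participant-by-stimulus, participant-by-regulation and participant-by-stimulus-by-regulation random effects (Aim 1 has no regulation factor, so those terms fall away there). This fallback pools the remaining person-level interactions into the residual, so it is the second choice. Use Kenward-Roger or Satterthwaite degrees of freedom. Do not use only a participant intercept and a participant-by-session effect.
- **Contrasts.** Test each hypothesis as its matching contrast. State that H2a and H2c use all placebo sessions and H2b all alcohol sessions.
- **Data handling.** Keep completed sessions of people who later withdraw or are stopped, and remove data only where the participant asks for it.
- **Reporting.** Give numbers and reasons for non-return by group and by first beverage.

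The cost is some extra model specification and no new data collection. The model still assumes that loss is explained by observed data, and it gains little for H1c and H2d.
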